1.0 EXECUTIVE SUMMARY

Relapse is inevitable in orthodontic treatment. Teeth will want to return to their original position after fixed appliances are removed. Regardless with or without fixed appliances, changes and physiological relapse will still occur due to time and age changes. This is why retention is a crucial part in orthodontic treatment, where it would aim to maintain the corrections achieved after orthodontic treatment.

Literature regarding retainers is quite substantial, where a recent Cochrane review was published comparing the different types of retainers. However, evidence is lacking in terms of comparison of arch width relapse between modified vacuum formed retainers and Hawley retainers specifically in expansion cases.

This study aims to compare the relapse in arch width in expansion cases with modified vacuum formed retainers with palatal coverage versus Hawley type retainers in Unit Ortodontik Universiti Kebangsaan Malaysia (UKM), Klinik Pakar Ortodontik Klinik Kesihatan Bandar Botanik and Unit Pakar Ortodontik Klinik Pergigian Sungai Chua patients. Although other types of modified vacuum formed retainers effective for maintaining palatal expansion have been described, these retainers require a wire outlining the Cementoenamel junction of the teeth palatally. This technique requires experience of the technician, is at a higher cost and requires more lab time. The modified retainer that we described in this study would be as efficient and as quick as the normal vacuum formed retainers, which would usually take a couple of hours to make (same day or next day fit). The present practice at all 3 locations constructs Hawley and normal VFR retainers for all orthodontic patients. There are technicians and laboratory facilities to construct normal VFR as well as Hawley retainer. The only difference between modified and normal vacuum formed retainer is the outline of the retainers where the technician would trim the retainer, where it would cover the hard palate. Therefore it is only the location of trimming that is different using the same special trimming appliances for normal VFRs.

A number of subjects who fulfil the criteria will be invited to participate in this study. The study will involve arch width analysis using study models pre, post-debond, 3 months review post-debond, 6 months review post-debond and 12 months review post-debond. All data will be analyses using Statistical Package for Social Sciences (SPSS). The arch width of subjects post-fixed appliances will be compared. Most studies compare the arch width, as well as lower incisor irregularity in evaluating relapse in different groups of retainers. However, there are currently no randomized control trials comparing expansion cases of Hawley vs vacuum formed retainers, hence why this study will be conducted.

We expect to see no difference between the modified vacuum formed retainer and Hawley retainer in terms of maintaining arch expansion post-orthodontic treatment. This would therefore mean that there would be a simpler method and would be a suitable more cost-effective alternative as compared to constructing Hawley retainers or adding a palatal wire on the vacuum formed retainers.

2.0 INTRODUCTION

Relapse is an unfortunate event post-orthodontic treatment. Around 70% of patients post-orthodontic treatment are subjected to relapse (1,2). Patients usually talk about retention in a negative light in social media(3), where the main themes expressed included compliance, impact, maintenance, patient-clinician relationship, and positive and negative feelings. It is therefore important to ensure that the retention regime is effective and convenient for the patient.

Arch expansion is a common modality of treatment in correcting posterior crossbites. Methods of expansion often used in removable/fixed appliances would include archwire expansion, quadhelix, rapid maxillary expansion or removable appliances with a midline screw. Surgical methods have also been described (SARPE- Surgical Assisted Rapid Palatal Expansion) for severe cases. Expansion of the arches is considered very unstable and prone to 40% of relapse, regardless of any type of expansion, and this is mostly due to post-treatment growth pattern of the patient (4,5).

There are various methods of retention, and a recent Cochrane review (6) has produced a very good summary and update of all the different types of retainers. In terms of expansion, a Hawley type retainer was indicated to be the best type of retainer to maintain expansion. In terms of material, acrylic is more durable than vacuum formed polyurethane material, which explains the property. There is limited evidence comparing the relapse in expansion between these two methods. This is mainly due to the fact that there is acrylic coverage of the palatal surfaces, as compared with a vacuum formed retainer where the coverage only extends a few millimetres beyond the cement-enamel junction of the palatal surfaces of the teeth. A modified vacuum formed retainer was described where the vacuum formed retainer was extended for palatal coverage, which in theory could maintain expansion better. Different versions of this modified retainer were described (7). The only difference in constructing the retainers would be the outline where the technician would trim the retainer, where it would cover the hard palate. **The use of this modified vacuum formed retainer was shown to be as effective as other methods of retention such as fixed bonded retainer (8)(9). The systematic review by Littlewood also showed that the normal vacuum formed retainer to be as effective as other retainers in terms of maintaining the inter-arch width (6).** However, the cases selected were normal Class 1 cases with normal antero-posterior and transverse skeletal dimensions, where our study would focus on expansion cases as the main subjects. Even with the robust evidence showing the strength of the vacuum formed retainer, clinicians in general still use the Hawley retainer in expansion cases with no existing clinical trial evaluating its effectiveness. However in the United Kingdom, there have been noted usage of this modified vacuum formed retainer in expansion cases, especially in emergency situations where retainers need to be made quickly.

Therefore, this study will focus on the relapse of arch width in two types of retention regimes, which are modified vacuum formed retainers and Hawley type retainers in patients after fixed appliance treatment. This will subsequently be of valuable information for clinicians in choosing the appropriate type of retainers after removal of their fixed appliances. This is because the modified vacuum formed retainers will be significantly

cheaper, quicker and easier to fabricate. There is a small risk of relapse using the modified vacuum formed retainers in expansion cases, however as mentioned earlier a lot of studies show good maintenance of arch width in normal cases (6)(8)(9). If relapse does occur, we anticipate that it will be minimal and a new retainer or retreatment can commence to easily rectify the situation as the patients are reviewed every 3 months. Other advantage is that most patients would prefer the appearance of vacuum formed retainers and superiority in terms of incisor alignment (6)(10). Literature showed that 40%-60% of allergic reaction was caused by formaldehyde (11). Formaldehyde may be released from methacrylate-based dental materials, such as composites and denture bases (12). An vitro study reported that there was minimal leaching of formaldehyde from thermoplastic materials (e.g. VFRs) while it was found higher leaching from poly-methyl methacrylate (PMMA) based orthodontic materials of the powder and liquid type (e.g. Hawley retainers) (13). Up to date, there is no reported case of sensitivity and contact allergy to VFRs while there was reported case of oral lesion in patient with Hawley retainer (14).

Hawley retainer		
Characteristics	Benefits	Risks
Clasps and wires anchored in a relatively thick plastic body	Personal opinion: suggested retainer to maintain expansion (Blake & Garvey 1998) compared with normal VFR (not modified)	More likely to break (Hichens et al. 2007)
Steel wire run across front teeth	More durable from patients' perception (Saleh et al. 2017)	Higher cost (Hichens et al. 2007) Require greater man power (Hichens et al. 2007) More difficult to fabricate (Saleh et al. 2017) Less aesthetic (Saleh et al. 2017) Heavier (Saleh et al. 2017)

Normal & Modified vacuum-formed retainer		
Characteristics	Benefits	Risks
Made up of thin and strong copolyester plastic sheets	Low cost (Hichens et al. 2007)	Less durable from patients' perception (Saleh et al. 2017) – Normal VFRs
Transparent	Easy to fabricate (Hichens et al. 2007)	
	Require less man power (Hichens et al. 2007)	
	More aesthetic (Saleh et al. 2017)	
	Lighter (Saleh et al. 2017)	
	Less likely to break (Hichens et al. 2007)	

Blake, M. & Garvey, M. T. 1998. Rationale for retention following orthodontic treatment. *Journal of the Canadian Dental Association* 64(9): 640–643. Retrieved from <http://www.ncbi.nlm.nih.gov/pubmed/9812432>

3.0 HYPOTHESIS

There is a difference in the degree of relapse in terms of relapse of arch expansion between Modified Vacuum formed retainers and Hawley retainers.

NULL HYPOTHESIS

There is no difference in the degree of relapse in terms of arch expansion between Modified Vacuum formed retainers and Hawley retainers.

[figure not shown]
4.0 AIMS AND OBJECTIVES

To measure the effectiveness of two different retainers in maintaining arch width post orthodontic treatment:

- i) Modified vacuum formed retainers
- ii) Hawley retainers

Measurement in terms of:

- i) Canine arch width
- ii) Premolar arch width
- iii) Molar arch width

5.0 METHODOLOGY

5.1 Participants Sampling

The sample will be selected from patients attending for orthodontic debond appointments at the Orthodontic Unit of Universiti Kebangsaan Malaysia (UKM), Klinik Pakar Ortodontik Klinik Kesihatan Bandar Botanik and Unit Pakar Ortodontik Klinik Pergigian Sungai Chua patients. The present practice at all 3 locations constructs Hawley and normal VFR retainers for all orthodontic patients. There are technicians and laboratory facilities to construct normal VFR as well as Hawley retainer. The only difference between modified and normal vacuum formed retainer is the outline of the retainers where the technician would trim the retainer, where it would cover the hard palate. Therefore it is only the location of trimming that is different using the same special trimming appliances for normal VFRs. Clinicians from KKM involved would be [name] [name] and [name] [name]. A screening will be done to select patients who are suitable of the study. Only patients who fulfil the criteria will be invited to participate in this study. Participant will be approached in the dental chair once deemed suitable, and will be given 5-10 minutes to decide on participation of the study. Consent will be gathered from the patients or the carer if the patient is below 18 years of age. The patients will then be randomly allocated into two groups using a randomized number computer generator, either the Hawley or the modified vacuumed formed retainers. The expected sample size to be of statistical significance will be calculated using the formula of sample size calculation relevant to this study. The sample size

calculation is based on a significance level of 0.05 and 80 percent power to detect a clinically meaningful difference of 2.0mm (SD=2.0mm) between the two groups in terms of arch width differences, where this difference are based on previous studies by Tynelius et al. (9) and Shawesh et al. (15). The power analysis gave a total sample size of 16 patients in each group. To account for attrition, 24 patients will be recruited in each group

The inclusion criteria of the subjects that will be included in the study are:

- a. Patients who are at least 13 years old at time of debond.
- b. Treatment plan of extraction or non-extraction followed by straight wire appliances in the upper arch only or both arches
- c. Undergone expansion treatment in the upper arch causing an arch width increase of 3-10mm, either using a Quadhelix, Rapid Maxillary Expansion, expansion with archwires, or URA with midline screw. Patients' interarch measurements at the time of debond will be compared with their interarch measurements using the pre-treatment model available at the clinic.
- d. No chronic medical conditions

The criteria for suspending or terminating the study are:

- a. Relapse due to compliance issue
- b. Relapse due to investigative product
- c. Subject did not come for follow-up

The subject withdrawal criteria are:

- a. Voluntary

If relapse is found and/or if subjects request to withdraw from the study, subjects will be informed that they will not need to take impressions at follow-up but they still can make appointment with their orthodontist for a normal retainer review. If insignificant relapse is found, new Hawley retainers will be provided free of charge. If significant relapse is found in subjects from intervention group, free treatment will be provided. The withdrawn subjects will not be replaced and an Intention to Treat analysis (ITT) will be done.

The generation of randomization sequence will be performed in blocks of 12 to ensure that equal number of patients was allocated to each of the two retention groups. A randomized generator will be used for allocation. In this multi-centre trial, a centralized randomization technique which incorporated external involvement is used. Individuals who recruit subjects from each centre will contact a central methods centre by phone after patient enrolled in order to prevent selection bias and protect the assignment sequence until allocation. Calibrated researcher will collect the study models which the ID and intervention are covered by opaque tape once they are ready for measurement. Only one dental cast at a time will be picked out of its box without showing any previous measurements. Two dental casts from the same patient will not be measured in connection with each other. Due to the prospective nature of the study, it was inconvenient to anonymize dental casts from the start of the study.

Hawley retainer
(coverage)

Normal VFR retainer

Modified VFR (palatal

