5.4 Data management and analysis

Intra-examiner reliability of the measurements will be undertaken on two occasions in a random order and following an interval of two weeks.

A normality test will be conducted to determine whether a parametric or non-parametric test should be conducted. The outcome measures assessed will be the differences in means between groups, which will be assessed by one-way analysis of variance, using Statistical Package for Social Sciences (SPSS) version 17.0.

[4] -- Monday, July 08, 2019 -- 15:58:42

F tests - ANOVA: Repeated measures, between factors

Analysis: A priori: Compute required sample size

Input: Effect size f	=	0.42
α err prob	=	0.05
Power (1-β err prob)	=	0.80
Number of groups	=	2
Number of measurements	=	3
Corr among rep measures	=	0.5
Output: Noncentrality parameter λ	=	8.4672000
Critical F	=	4.1708768
Numerator df	=	1.0000000
Denominator df	=	30.0000000
Total sample size	=	32
Actual power	=	0.8038973

A reliability test will also be performed to calibrate the measurements made. The data will be reported in a collective manner with no reference to the specific individual. Publication policy by most journals would require removal of any personal details of any patient in any part of the article or in any supplementary materials (including all illustrations and videos) prior to submission, therefore the personal information from each individual will remain confidential. Access to the data is only by the research team (which involves orthodontists, dentists, personnel) and the REC UKM and KKM. The hard copy of the data obtained will be stored in a locked cupboard in a private room that could only be accessed by the research team. Soft copy of the data will be contained in a USB protection lock which password is only known to the research team. Data will be allowed for inspection or auditing by regulatory authorities. Data could be stored for at least 7 years before being destroyed (shredded) or deleted (electronic copy). Individuals have a right to know the results of their study and can contact the researchers if interested.

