5.4.1 Dental casts

Dental casts of four occasions will be obtained, on the day of removal of orthodontic appliances (T0), 3 months post- removal of orthodontic appliances (T1), 6 months post-removal of orthodontic appliances (T2) and 12 months post-removal of orthodontic appliances (T3). Based on a previous study (9), linear measurements will be made with an electronic digital calliper on the dental cusps to a precision of 0.01mm:

- Intercanine width in the maxilla- the distance between the canine cusp tips
- Interpremolar width in the maxilla- the distance between the premolar cusp tips
- Intermolar width in the maxilla- the distance between the mesiobuccal cusp tips of the first molars

Landmarks of cusp tips are identified based on guidelines described in the literature, where the most prominent tip is selected (9). If attrition is present, the centre of the surface area is determined to be the point of measure.

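### The sample size text, the printed power output and the named analysis use two effect sizes and two models, so the printed 80.4% is not the power of the one-way ANOVA the plan names

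*Combined protocol and SAP*

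**What the plan says.** Three statements bear on this.

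- **Section 5.1, sample size text.** The significance level is 0.05 and the plan claims "80 percent power to detect a clinically meaningful difference of 2.0mm (SD=2.0mm) between the two groups". The result follows: "The power analysis gave a total sample size of 16 patients in each group". Recruitment is raised to 24 per group for attrition. No test is named here.
- **Section 5.4, printed output.** The calculation is headed "F tests - ANOVA: Repeated measures, between factors". Its inputs are effect size f = 0.42, alpha 0.05, power 0.80, two groups, three measurements, and 0.5 for "Corr among rep measures". It returns a total of 32 patients and an actual power of 0.8038973.
- **Section 5.4, analysis.** The outcome is the difference in means between groups, "which will be assessed by one-way analysis of variance".

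Section 5.4.1 adds that "Dental casts of four occasions will be obtained" (T0 to T3). The plan does not derive f = 0.42 from 2.0 mm and SD 2.0 mm, give a source for the correlation, say which three measurements the output refers to, or name a repeated-measures ANOVA as the analysis.

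**The concern.** A difference of 2.0 mm with SD 2.0 mm corresponds to f = 0.50 for two equal groups, not 0.42. A repeated-measures between-factors test is also not the same as a one-way ANOVA on a single value per patient: it gains power by combining visits, and that gain depends on the correlation between them. The sample size text, the output and the analysis therefore do not describe one calculation.

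This matters because the executive summary expects no difference between the retainers, and section 5.3 would let participants take silence about the results to mean that the modified retainer is as good. A null result can be read only against the difference the trial could detect. The plan leaves that difference unclear, along with the model that carries the 80%.

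**Working it through.** **Inputs.** From 5.1: alpha 0.05, power 80%, difference 2.0 mm, SD 2.0 mm, 16 per group (24 recruited). From the output in 5.4: f = 0.42, m = 3 measurements, correlation ρ = 0.5, N = 32. Tests are taken as two-sided, because the hypothesis in section 3.0 is non-directional. I assume that SD 2.0 mm is the SD of the value analysed.

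**1. The printed output reproduces.** For the between-groups test in a repeated-measures ANOVA, λ = f²·N·m / [1 + (m − 1)ρ], with 1 and N − 2 degrees of freedom.

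λ = 0.1764 × 32 × 3 / 2 = 8.4672; critical F(1, 30) = 4.1709; power = 0.8039. This matches the output.

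**2. The text's 16 per group also reproduces, by another route.** The normal-approximation formula for two means gives n = 2 × (1.960 + 0.842)² × (2.0/2.0)² = 15.70, rounded up to 16 per group (approximate power 80.7%).

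**3. The effect sizes differ.** For two equal groups f = d/2.

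- Text: d = 2.0/2.0 = 1.0, so f = 0.50.
- Output: f = 0.42, so d = 0.84. That is 0.84 × 2.0 = 1.68 mm at SD 2.0 mm, or 2.0 mm at SD 2.0/0.84 = 2.38 mm.

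Putting the text's f = 0.50 into the printed model gives 0.7996 at N = 23 and 0.818 at N = 24. That model would have returned 24 patients in total, not 32, so the output is not the calculation described in 5.1.

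**4. Power of a one-way ANOVA on one value per patient.** Here λ = f²·N, with 1 and N − 2 degrees of freedom. At N = 32 and f = 0.50, λ = 0.25 × 32 = 8.0.

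| Evaluable per group | f = 0.50 | f = 0.42 | Difference detectable with 80% power, SD 2.0 mm |
|---|---|---|---|
| 16 | 78.1% | 63.3% | 2.05 mm |
| 17 | 80.7% | – | 1.98 mm |
| 24 | 92.4% | 81.3% | 1.65 mm |

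At f = 0.42, 23 evaluable per group give 79.6%, so 80% needs all 24.

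**5. Dependence of the repeated-measures model on the correlation (m = 3).** Only ρ = 0.5 is in the plan; the other values are an assumed range.

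| | ρ = 0.3 | ρ = 0.5 | ρ = 0.7 | ρ = 0.9 |
|---|---|---|---|---|
| f = 0.42, 16 per group | 88% | 80% | 73% | 66% |
| f = 0.50, 16 per group | 96% | 92% | 86% | 81% |
| f = 0.42, 24 per group | 97% | 94% | 89% | 84% |

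**The case against.** The strongest reply is that nothing has been miscalculated. Both routes reach 16 per group, and with two groups the between-factors test is mathematically a one-way ANOVA on each patient's mean over the three measurements, with the same degrees of freedom, λ and power. On that reading the 80.4% would be the power of a one-way ANOVA. The equivalence is real, but the plan describes no averaging over visits, and 5.4 does not say what value per patient enters the test. It shows one way to repair the plan, not what the plan says.

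Other points stand as qualifications:

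- The output gives no SD, so 1.68 mm is conditional on SD 2.0 mm. Keeping 2.0 mm implies SD 2.38 mm, which still contradicts 5.1.
- The three measurements could be changes from T0 at T1, T2 and T3. They could also be the three casts at T0, T1 and T2, since the visit table in 5.2 lists only those visits. The plan does not settle this.
- A correlation below 0.5 would raise power, so the dependence runs both ways.
- The 63.3% combines the output's effect size with a single-value test, a pairing the plan does not state. On the stated 2.0 mm the shortfall is small and recruitment already exceeds it.

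These points limit the size of the problem but do not remove the mismatch.

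**Conclusion.** The concern holds. The 80.4% belongs to a repeated-measures model at f = 0.42. The plan names a one-way ANOVA and justifies its sample size with 2.0 mm and SD 2.0 mm (f = 0.50).

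For the stated difference, the practical gap is about 2 points of power, or one patient per group (78.1% at 16, 80.7% at 17). It becomes large, at 63.3%, only if f = 0.42 is the intended target and the one-way test uses one value per patient. If all 24 per group are evaluable, power is above 80% in every combination shown. That margin is not assured: the additional eight per group are there for attrition, 5.1 ends study impressions once relapse is found, and 5.3 counts a broken retainer as a dropout. In the least favourable case (f = 0.42, one-way test), losing one patient per group takes power just below 80%.

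These figures rest on two-sided testing at 0.05, equal groups, and 2.0 mm being the SD of the analysed value. The inconsistency should be corrected before data are analysed, so that the model is not chosen after the results are seen.

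**What to change.** Keep 24 recruited per group and adopt one of two options. Either way, name the arch width (canine, premolar or molar) to which the power statement applies.

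1. **Single-visit comparison (simplest).** Replace the statement in 5.1 with: *Two-group comparison (one-way ANOVA) of change from T0 in [named width] at [named visit]; difference 2.0 mm, SD of change 2.0 mm, two-sided 0.05. 16 evaluable patients per group give 78% power, 17 give 81% and 24 give 92%.* Delete the repeated-measures output from 5.4.
2. **Repeated-measures analysis.** Make the between-group test on change from T0 at T1, T2 and T3 the primary analysis in place of the one-way ANOVA, and align the visit table in 5.2 with the four casts in 5.4.1. State the effect in millimetres (1.68 mm at SD 2.0 mm if f = 0.42 is kept). Show power at 32 patients for correlations of 0.5, 0.7 and 0.9: 80%, 73% and 66% at f = 0.42, or 92%, 86% and 81% at f = 0.50.

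The cost is wording and restated figures, with no increase in the recruitment target and no visits beyond the four casts already in 5.4.1. Option 1 means stating 78% instead of 80% at 16 per group. Option 2 commits the plan to one longitudinal model and makes its dependence on the correlation visible.

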5.2 Study design

This is a prospective randomised controlled trial to evaluate the differences in relapse after expansion treatment between a Hawley and a modified vacuum formed retainer.

The study will involve:

- a. **Clinical:** An upper and lower impression with alginate will be taken for dental cast and retainer construction. **This procedure is a normal procedure done in all orthodontic appointments upon removal of fixed appliances.** However one extra upper impression will be taken for the research. It will take approximately 5-10 minutes. **All retention appliances will be distributed within 24 hours after debonding. The retainers will be washed under tap water before delivering to the patient. When subjects are given the retainers, clinicians will provide post-debond instructions, where the patient has to wear the retainers for 24 hours except during eating and brushing their teeth. Researcher will send reminders of wearing retainer in 1-month interval to ensure they are following the instructions and to enquire if they have any problems.** The patients will be instructed to wear the retainers for 24 hours for the next 6 months and night-time only for month 7 to month 12. At a 3 month and 6 month follow-up, an upper alginate impression will be taken for a dental cast construction at each follow-up visit. **Clinical examination will allow clinician to detect relapse which is by examining the arch width.** The whole duration of participation of each patient may total up to 40 minutes overall. If any unknown allergic reaction to alginate impression occurs, the procedure will be terminated immediately and appropriate first aid action will be given to participant, however these will most likely be anticipated as these subjects have had impressions taken at the start of treatment.
- b. **Data Measurement:** Dental casts will be analysed using digital callipers and arch width will be recorded in the posterior region.
- c. **Data analysis:** Data will be analysed using SPSS. The descriptive statistics on group level at times corresponding to measurements at removal of fixed appliances (T0), 3 months post retention (T1), 6 months post retention(T2) and 12 months post retention(T3) will be calculated for each variable.

RELAPSE DUE TO POOR COMPLIANCE:

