- Poor compliance can be detected by the clinician, such as poor adaptation to speech, appliance looks “clean”, patient unable to seat and remove the appliance, or appliance is lost and not looked after properly.
- Arch width reduced
- Retainer will not fit in mouth

RELAPSE DUE TO INTERVENTION

- Patient able to adapt to retainers well, good adaptation to speech, appliance looks used, patient able to seat and remove retainers easily
- Arch width reduced
- Retainer should still fit in the mouth if patient wears it all the time

Compliance can be confirmed by the use of Thermosensors. Thermo-sensor is not used in this study because it is costly, not entirely accurate and it will not reflect the real-life situation. Most clinical studies do not use Thermosensors to ensure compliance. Using sensors will give out the Hawthorne effect where subjects will tend to perform better since they are aware of the presence of thermos-sensors. This as mentioned earlier does not reflect the real-life scenario.

Monitoring for adverse events

T0: Removal of braces	T1: 3-month review	T2: 6-month review
-Duration: 10-20 minutes -Subjects who have had 3mm of expansion (compared with pre-treatment models) will be selected, subjects given 5-10 minutes to think if they want to participate -Impression will be taken for construction of retainer and study models which will take 5-10 minutes -Adverse reaction i.e. allergic reaction to the impression material will be monitored however this would have been anticipated or recorded in the notes as these patients	-Duration: 5-10 minutes -Subjects will be reviewed and any adverse effect such as relapse will be detected at this point -An upper impression will be taken -Adverse reaction i.e. allergic reaction to the impression material will be monitored however this would have been anticipated or recorded in the notes as these patients would have had impressions taken at the start of orthodontic treatment. -If any allergic reaction occurs, first aid	-Duration: 5-10 minutes -Subjects will be reviewed and any adverse effect such as relapse will be detected at this point -An upper impression will be taken -Adverse reaction i.e. allergic reaction to the impression material will be monitored however this would have been anticipated or recorded in the notes as these patients would have had impressions taken at the start of orthodontic treatment. -If any allergic reaction occurs, first aid

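### Subjects found to have relapsed, the trial's own outcome, are released from later casts, and the promised ITT analysis has no rule for the casts that may then be missing

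*Combined protocol and SAP*

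**What the plan says.** The null hypothesis (section 3.0) concerns the degree of relapse of arch expansion, so relapse is the outcome.

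Section 5.1 includes "Relapse due to investigative product", and relapse from poor compliance, among the criteria for suspending or terminating. On later visits it continues: "If relapse is found and/or if subjects request to withdraw from the study, subjects will be informed that they will not need to take impressions". It then says: "The withdrawn subjects will not be replaced and an Intention to Treat analysis (ITT) will be done". On numbers it says: "To account for attrition, 24 patients will be recruited in each group", up from 16.

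Section 5.2 says how relapse is found: "Clinical examination will allow clinician to detect relapse which is by examining the arch width". Its lists for attributing relapse to compliance or to the retainer both include "Arch width reduced", with no size in millimetres. The monitoring table for the 3- and 6-month reviews reads "any adverse effect such as relapse will be detected at this point -An upper impression will be taken".

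Section 5.4 names a normality test and one-way ANOVA on group means. Its power output is for a repeated-measures test with 3 measurements. Nothing is said about missing casts. Section 5.3 treats a subject whose retainer breaks as a dropout.

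**The concern.** Subjects may leave the measured set because of the value being measured. If one retainer relapses more, that arm loses more of its worst later values, and those who remain look more alike than the randomised groups are.

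ITT fixes the arm in which a subject is counted; it does not create a cast that was not taken. Going from 16 to 24 per group restores precision but does not undo selective loss.

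Measurement is masked ("study models which the ID and intervention are covered by opaque tape once they are ready for measurement"), but the finding of relapse is not described as masked. It is made at a clinical examination that also looks at fit and signs of wear, so the clinician presumably knows the retainer type. The same reduction could therefore be called relapse more readily in one arm.

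The conclusion is at stake. The Executive Summary expects no difference, and section 5.3 would take the absence of a reported difference to mean that the modified retainer is as good as the Hawley. Casts not taken cannot be recovered, and without a rule their handling would be chosen after the data are seen.

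**Working it through.** **The plan's own figures.** From section 5.1: difference 2.0 mm, SD 2.0 mm, alpha 0.05 (two-sided assumed), power 80%. n = 2 × (1.960 + 0.842)² × (2.0/2.0)² = 15.7, so 16 per group, as stated. From section 5.4: λ = 0.42² × 32 × 3 / (1 + 2 × 0.5) = 8.4672, critical F(1, 30) = 4.1709, power 0.8039, as printed. The sample size is not in error. With 24 per arm all cast, a t test has 92% power. Recruiting 24 allows for a loss of 1 − 16/24 = one third, at random.

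**Assumptions not in the documents.** Relapse is normal. Mean relapse is 1 mm in one arm and 3 mm in the other at T3, either present from T1 (early) or building up evenly (0.33, 0.67, 1 v 1, 2, 3; accumulating). A subject is released after the first review with relapse of at least c, for c = 2 to 5 mm. Every released subject is lost after that visit. Correlation between visits is 0.5 (the section 5.4 value) unless stated.

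**T2, closed form.** The mean at T2 among those not released at T1 is m₂ − ρ × SD × φ(z)/Φ(z), with z = (c − m₁)/SD.
- Early, c = 2: 1 − 0.5 × 2 × 0.509 = 0.49, and 3 − 0.5 × 2 × 1.141 = 1.86. Difference 1.37 mm, not 2.0. Expected remaining: 24 × 0.691 = 16.6 and 24 × 0.309 = 7.4.
- Early, c = 5: (3 − 0.288) − (1 − 0.055) = 1.77 mm.
- Accumulating (true difference 1.33 mm): c = 2 gives 1.33 − (0.509 − 0.353) = 1.18 mm; c = 5 gives 1.33 − (0.055 − 0.026) = 1.30 mm. With triggers of 3 to 5 mm, power is 52–61% against 62% with all casts.

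**T3, simulation (at least 4,000 trials per setting), remaining subjects, true difference 2.0 mm.**

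| Trigger | Early: difference, power (left per arm) | Accumulating: difference, power (left per arm) |
|---|---|---|
| 2 mm | 1.13 mm, 16% (13.1 v 3.9) | 1.61 mm, 54% (15.6 v 10.1) |
| 3 mm | 1.27 mm, 34% (17.9 v 8.0) | 1.70 mm, 73% (19.7 v 15.0) |
| 4 mm | 1.45 mm, 56% (21.2 v 13.1) | 1.80 mm, 83% (22.3 v 19.4) |
| 5 mm | 1.63 mm, 75% (23.0 v 17.9) | 1.89 mm, 89% (23.4 v 22.1) |

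This is not only smaller numbers: with early relapse and a 3 mm trigger, an unbiased comparison of the same numbers would have about 62% power, not 34%.

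**What changes the answer.**
- Correlation 0: no bias, only lost numbers.
- Half of released subjects, at random, still cast (any effect of a refit ignored): T3 about 1.8–2.2 mm with early relapse, power 78–89%; 1.86–2.04 mm with accumulating relapse, power 78–92%. These runs also cover a 1 mm trigger and correlation up to 0.8.
- Equal arms, same trigger: no bias, about 5% rejections.
- Equal arms (both 2 mm), triggers 2 v 4 mm, T2: (2 − 0.288) − (2 − 0.798) = 0.51 mm; at correlation 0.8, 1.6 × (0.798 − 0.288) = 0.82 mm. This false difference favours the arm with the 2 mm trigger and gives 11–24% rejections.
- True 2.0 mm difference, 2 mm trigger in the better arm and 4 mm in the worse, T3: about 2.0 mm (early) or up to about 2.3 mm (accumulating).

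**Can a model repair it?** A likelihood model on all casts up to and including the detecting visit returns 1.98–2.03 mm at T3 for triggers of 2 to 5 mm (correlation 0.5 or 0.8). Its power is 27–91% (early) or 64–92% (accumulating). It removes the bias but not all the loss of precision.

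**The case against.** The wording is a release, not a ban, so some released subjects may still be cast, and the shrinkage largely goes if about half are. This stands, and it limits what can be said about size.

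The review table lists an impression at each review, so the cast at the detecting visit is probably taken. This also stands: a comparison at that visit is largely protected, although no sentence guarantees the cast for a released subject.

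ITT is promised, and nowhere does the plan say that only remaining subjects will be compared. That is correct. The documented defect is ITT with no rule for casts the protocol itself makes optional; the comparison of remaining subjects is one way the gap could be filled.

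The reduced-width item in section 5.2 helps attribute relapse to a cause and is not presented as the release threshold. The Introduction also expects any relapse to be minimal. Both are fair, which is why a range of triggers is shown.

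A reader might infer that the rule is bound to hide a true difference, or that every later cast of a relapsed subject will be lost. The documents support neither. The direction depends on correlation and on even-handed calling of relapse, and the extent depends on how many released subjects are still cast.

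**Conclusion.** The concern holds in a conditional form. The protocol makes later casts optional because of the outcome, and neither ITT, ANOVA nor the larger recruitment target deals with the gap.

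Pull toward no difference needs three conditions: most later casts of released subjects are lost, visits are positively correlated, and relapse is called alike in both arms. The effect is then severe with early relapse and a low trigger, and small with a high trigger and accumulating relapse, particularly at T2. With uneven calling, the bias can run either way, including a false difference between equal arms. All sizes rest on assumed means and triggers.

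If impressions end at 6 months, as the clinical schedule in section 5.2 implies, the problem concerns T2 only. Any bias from counting breakage as dropout is of unknown direction and is not quantified.

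This should be fixed. Confidence is high that the rule and the gap exist, and moderate on size.

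**What to change.** - In section 5.1, delete relapse as a reason to stop study casts. In section 5.3, do the same for breakage counted as dropout.
- State that the upper cast is taken at the visit where relapse or breakage is found, before any replacement or retreatment, and that scheduled casts continue for every randomised subject who agrees.
- In section 5.4, analyse all randomised subjects by allocated arm with a prespecified repeated-measures mixed model (arm, visit, arm-by-visit). Include all casts taken, to honour the promised ITT.
- Alongside it, report the same model limited to casts before any refit or retreatment, including the detecting-visit cast, as the measure of retention by the allocated retainer. The two answer different questions, so state in advance which is primary.
- Report relapses, breakages, refits and retreatments by arm and visit.
- Reconcile sections 5.1 and 5.3, which describe management after relapse differently. Reconcile the 12-month cast (sections 1.0 and 5.4.1) with the impressions in section 5.2, which stop at 6 months. Care decisions stay with the investigators.

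Cost: protocol wording, plus one or two already scheduled 5–10 minute impressions per subject with relapse. That could be many subjects if small reductions count as relapse: with early relapse and a 2 mm trigger, (24 − 13.1) + (24 − 3.9) = about 31 T3 casts are at issue. The model limited to casts before refit also assumes that loss depends on recorded widths.
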